### 3.1.6 Randomization

After baseline testing and within 2-4 months of completing CRT, patients meeting criteria for randomization (see [Section 4.2](#)) will be assigned to either **Arm A** (adaptive testing) or **Arm B** (non-adaptive testing). Randomization will be stratified by age (< 8 vs.  $\geq$  8 years), treatment intensity (whole brain vs. focal radiation) and Coach (A vs. B). Note: the patient's coach assignment can be found on the Eligibility form receipt in eRDES (the field is auto-populated by the system after the form has been validated and saved). *Coach A or B assignment at enrollment should not be confused with the assignment to treatment Arm A or B at randomization.*

Treatment randomization is accomplished by completing the Callback in eRDES (refer to instruction on the Case Report Forms for details). The Callback must be completed prior to initiation of study treatment.

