### 6.0 STATISTICAL CONSIDERATIONS

#### 6.1 Statistical Design

This primary goal of the study is to establish feasibility of a home-based computerized cognitive training program *Cogmed*, on patients 6 to 16 years of age with pediatric brain tumors and undergoing CRT. Within approximately 2-4 months of completing CRT, patients meeting criteria for randomization will be randomized 1:1 to Arm A the intervention arm (adaptive program) or Arm B the active control arm (non-adaptive program). Randomization will be stratified by known risk factors including age (< 8 years vs.  $\geq$  8 years), treatment intensity (whole brain vs. focal RT) and also by Coach (A versus B). Randomized patients are expected to complete 25 training sessions over 5 to 9 weeks, and then complete a post-

intervention testing and a 6-month follow-up testing. The treating psychologist and/or the individual performing computerized cognitive testing must be blinded for testing.

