## 6.2 Patient Accrual and Expected Duration of Trial

The study accrual target is 60 randomized patients evaluable for the primary endpoint of intervention compliance. It is anticipated that some children who complete the baseline assessment will not meet the eligibility criteria for randomization based on evidence of intellectual disability or psychiatric functioning. In the trial of *Cogmed* with survivors, less than 10% of children screened were excluded from participation for these reasons.

Randomized patients who are removed off protocol therapy for medical reasons (relapse/progression, death, physician's determination in the patient's best interest, development of seizures or other change in functional status, or starting or changing the dose of psychostimulants) would be deemed inevaluable for the primary compliance endpoint. Therefore, using an estimate of 15% for screen failures and inevaluable patients, we project that we may need to enroll up to 71 participants.

With enrollment open to all institutions within COG, we anticipate that our goal of accruing 60 evaluable patients from those eligible is feasible within two years after Amendment #1 is activated. There are very few on-therapy cognitive intervention trials from which to base an estimate of feasibility, though at St. Jude Children's Research Hospital, recruitment to SJMB03, which has a reading-based intervention program embedded in the study, was strong. Specifically, 64% of children enrolled on the protocol have been randomized to either the treatment or standard-of-care arm of that protocol. The primary reasons that children were not randomized, in order of frequency, included 1) age outside the inclusion criteria, 2) poor medical status (including posterior fossa syndrome), 3) non-English speaking, and 4) parents did not consent to randomization ([name], study PI, personal communication on Oct. 29, 2010). We anticipate that parents of children receiving cranial radiation therapy will be aware of the potential risks of neurocognitive late effects, and that at least one quarter of these parents will be willing to have their children participate in a cognitive intervention trial, particularly since it is home-based. The project has the strong support of the Behavioral Sciences Committee, and we have identified key personnel at each site who can help to inform colleagues about the study and motivate referrals of eligible patients.

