### 6.3.2 Power Considerations

Because there is no evidence that a home-based, computerized CT program will be feasible for this population and in multiple COG institutions, our primary aims are to evaluate the program's ease of use and participant compliance, which we will define as 80% of sessions completed within 9 weeks of starting treatment. The goal is to have at least 75% of participants being compliant (i.e., completing 20 or more of the 25 sessions). Randomized patients who are removed off protocol therapy for medical reasons (relapse/progression, death, physician's determination in the patient's best interest, development of seizures or other change in functional status, or starting or changing the dose of psychostimulants) would be deemed inevaluable for the primary compliance endpoint. With 60 evaluable participants, if the true compliance rate in the study participants is 59%, the power to detect such decrease from the target 75% compliance rate is 0.82. Power consideration is based on a Z-test for binomial proportion with continuity correction at 1-sided level of 0.05.

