### 6.3.3 Analysis Plan

Compliance rate (the portion of patients who complete at least 80% of the sessions within 9 weeks) will be calculated for the overall study population and each arm separately. Z-test for binomial proportion with continuity correction will be used to examine if the overall compliance rate is lower than the target of 75%. Confidence intervals of the estimated compliance rate will be constructed for the overall study population and for each arm separately. We will use Fisher's exact test to examine if there is any significant difference in the compliance rate between the 2 arms. Compliance data on the number of sessions completed for all patients and for patients on each arm will also be described by summary statistics such as mean or median, and compared between the 2 arms by two-sample t-test or Wilcoxon rank sum test. We will use descriptive and summary statistics to report parent and child ratings of the intervention's technical feasibility, ease-of-use, and satisfaction across the three time-points that this information is collected. In addition, we will use descriptive and summary statistics to detail the total number of patients enrolled, determine rates and reasons for non-eligibility and patient refusal for randomization, characterize socioeconomic status of the parents and computer usage for the patients and evaluate the number and type of adverse incidents reported through the questionnaires (if any). We will use a series of t-tests (for continuous variables) and Chi-square tests or Fisher's exact tests (for non-continuous variables) to examine potential differences between eligible patients who accept or decline to be randomized to the treatment phase, between participants who are compliant (i.e., 80% of sessions completed) and noncompliant, and for other medical, psychosocial, and contextual factors.

The analysis of preliminary efficacy will be conducted on an intent-to-treat basis. We will use descriptive/summary statistics to summarize the objective and the subjective measures of attention and WM in each arm and the differences between the 2 arms on the post-intervention/6-month assessment or on the difference between the post-intervention/6-month assessment and the baseline assessment. Linear regression models using the post-intervention/6-month assessment as outcome will also be used to estimate the effect size of intervention with adjustment for potential confounders including the baseline assessment. Linear

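### The exploratory effect-size models do not commit to adjusting for the three factors that stratify randomization, so their standard errors may be conservative

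*Combined protocol and SAP*

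**What the plan says.** Sections 3.1.6, 4.1 and 6.1 stratify the 1:1 allocation by age (below 8 against 8 or older), radiation field (whole brain against focal) and coach (A against B). Section 6.1 gives the reason: "Randomization will be stratified by known risk factors including age". Treatment intensity is listed with age, and coach is added separately.

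The efficacy analysis is in Section 6.3.3. The linear regression takes the post-intervention or 6-month score as outcome and estimates the arm effect "with adjustment for potential confounders including the baseline assessment". Baseline is the only covariate named, and there is no list or selection rule for others. The mixed model is something to be considered. It is described as handling the dependence of repeated measures within a patient, and no covariates are named for it. Age and socioeconomic status appear at the end of the section, in exploratory regressions of what predicts feasibility, acceptability and short-term efficacy. Radiation field and coach are not named as covariates in any model.

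Section 1.2 makes this aim exploratory: to estimate an effect size for designing a definitive trial. Section 6.3.3 specifies confidence intervals for the compliance rate but none for the efficacy effect sizes.

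**The concern.** The analysis of a stratified trial should normally reflect how it was randomized. Stratified allocation makes the arms alike on the stratifying factors, which reduces the true sampling variation of the arm difference. A linear model without those factors still counts their contribution as residual noise, so it reports a larger standard error than the design earned.

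The wording makes that outcome possible. The criterion for entering the regression is confounding, and factors balanced by design are not confounders in the usual sense. An analyst could follow the text properly and omit all three.

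What is at stake is the one product of the efficacy aim: an effect size, with its uncertainty, to be carried into the design of a larger trial. An open covariate list also lets that estimate depend on choices made after the data are seen, across several outcomes, two post-baseline times and two model types.

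**Working it through.** **The plan's own figure.** The documents give no power or precision for the efficacy models. The only such figure is for compliance (Section 6.3.2): "if the true compliance rate in the study participants is 59%, the power to detect such decrease from the target 75% compliance rate is 0.82".

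- Critical proportion, one-sided 0.05 with continuity correction: 0.75 − 1.645 × √(0.75 × 0.25/60) − 1/(2 × 60) = 0.6497.
- Standard error at 59%: √(0.59 × 0.41/60) = 0.0635.
- Power: Φ((0.6497 − 0.59)/0.0635) = Φ(0.940) = 0.827, against 0.82 stated.

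Enrollment also reproduces: 60/0.85 = 70.6, so 71. Neither figure depends on the efficacy covariates.

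**Inputs for the efficacy models.**

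- From the documents: 60 patients (Section 6.2), 1:1 allocation (Section 6.1), and three two-level factors, hence eight strata (Section 3.1.6).
- Assumed: R², the share of variance remaining after baseline that the three factors explain, taken from 0 to 0.30.
- Assumed for the simulation: 25% of patients under 8, 50% whole brain, 50% Coach A, permuted blocks of 4, baseline-to-outcome correlation 0.6.

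The 60 counts patients evaluable for compliance. The efficacy set could differ, so 40 was also examined.

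**Formula.** With balanced arms, the ratio of 95% interval widths for the arm effect, omitting against including the three factors, is

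t(0.975, N−3) / [t(0.975, N−6) × √(1 − R²)].

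At N = 60, t(57)/t(54) = 2.0025/2.0049 = 0.999. At R² = 0.10 the ratio is 0.999/√0.90 = 1.053.

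**Results at N = 60** (simulation: 4,000 replicates per row).

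| Assumed R² | Ratio, formula | Ratio, simulated | Coverage without factors | Coverage with factors |
|---|---|---|---|---|
| 0 | 0.999 | 0.995 | 94.6% | 94.6% |
| 0.05 | 1.025 | 1.021 | 95.8% | 95.2% |
| 0.10 | 1.053 | 1.050 | 96.0% | 95.2% |
| 0.20 | 1.117 | 1.114 | 96.6% | 94.7% |
| 0.30 | 1.194 | 1.193 | 97.7% | 95.2% |

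The Monte Carlo standard error of a coverage near 95% is √(0.95 × 0.05/4000) = 0.3 points, so the coverage shift at R² = 0.05 is barely distinguishable. A separate run with baseline correlation 0.77 and 8,000 replicates gave ratios of 1.022, 1.051 and 1.115 at R² of 0.05, 0.10 and 0.20, with coverage of 95.7%, 96.2% and 96.9%. The result hardly depends on the baseline correlation.

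**Where the excess width comes from.** At R² = 0.20 the mean interval width without the factors is 0.835, so the reported standard error is about 0.835/(2 × 2.0025) = 0.208. The estimate's actual standard deviation across replicates is 0.192. With the factors, the figures are 0.750/(2 × 2.0049) = 0.187 and 0.189. The estimator itself is almost equally precise either way (0.192 against 0.189). The model without the factors misreports that precision.

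**Cost if the factors explain nothing.** At R² = 0, including them widens the interval by 0.1% (formula) or 0.5% (simulation) at N = 60. At N = 40 the simulated ratio is 0.987, or 1.3% wider.

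**The case against.** The strongest reply is that the text leaves the covariate set open. Baseline is given as an example, and the plan itself calls the first stratification factors known risk factors, so they are natural candidates for adjustment. Section 6.3.3 also names age among predictors to be examined. This stands: the factors are unnamed, not excluded. A reader might infer that the models leave them out, but the documents do not say so.

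The second reply is that the size is conditional. The documents give no R². Baseline adjustment absorbs much of the variation between children, CogState scores are already age-standardized (Appendix III), and nothing in the documents shows that coach predicts cognitive scores. This also stands, and it is why the range must include zero. It does not make zero the likely value for every factor. Section 2.1 describes larger declines in children treated younger, and Section 2.2 presents intervention on treatment as acting before decline occurs. A baseline score taken 2 to 4 months after radiation cannot fully carry later decline that differs by age or radiation field. The age cut also matches the change of program version at 8 years (Section 4.4).

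Third, no efficacy interval, test or power is specified, so the coverage figures describe intervals the plan never defines. That is correct. The same standard errors would nevertheless underlie any statement of uncertainty around the effect size.

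Finally, the open list permits covariates to be chosen after seeing the data, but Section 6.3.3 describes no such search. A reader might infer that one is planned; the text does not support that.

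**Conclusion.** The point holds in a limited form. The effect-size models do not commit to the three factors by which the trial randomizes. If those factors are prognostic beyond baseline, standard errors that omit them are conservative. At 60 patients the excess interval width is about 0%, 2%, 5% or 12% for an assumed R² of 0, 5%, 10% or 20%, with coverage of about 95% to 97%. R², block size, stratum proportions and baseline correlation are all assumptions.

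Two stronger readings should be set aside. One is that intervals will certainly be too wide: this depends on an R² that the documents do not give and that could be near zero for some outcomes. The other is that the arm effect would be biased: in a linear model after randomization, leaving out these factors does not bias it. The aim is exploratory, and the compliance endpoint, its test and its 0.82 power are unaffected. The case for change rests on a small, possible gain at almost no cost, together with less room for discretion in the estimate that the next trial will use.

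**What to change.** Add a sentence to Section 6.3.3: the linear regression and the mixed model for the arm effect include arm, baseline score, age group (below 8 against 8 or older), radiation field and coach as fixed effects. In the mixed model, baseline may enter as a covariate or as the baseline timepoint; say which. Use main effects only, since eight strata average 60/8 = 7.5 patients each. Label any model with further covariates as exploratory. The planned look at age and socioeconomic status as predictors can stay under that label.

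The cost is wording and three degrees of freedom (57 to 54 in the regression at N = 60). All three factors are already recorded for randomization, so no new data are needed. If they turn out to explain nothing, the loss is at most about 1% in interval width.

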#### 6.4 Gender and Minority Accrual Estimates

The gender and minority distribution of the study population is expected to be:

Racial Categories	DOMESTIC PLANNED ENROLLMENT			
	Ethnic Categories			
	Not Hispanic or Latino		Hispanic or Latino	
	Female	Male	Female	Male
Total				
American Indian/ Alaska Native	0	0	0	0
Asian	1	0	0	0
Native Hawaiian or Other Pacific Islander	0	0	0	0
Black or African American	4	5	0	0
White	16	27	3	5
More Than One Race	0	0	0	0
Total	21	32	3	5
				61

Racial Categories	INTERNATIONAL (including Canadian participants) PLANNED ENROLLMENT			
	Ethnic Categories			
	Not Hispanic or Latino		Hispanic or Latino	
	Female	Male	Female	Male
Total				
American Indian/ Alaska Native	0	0	0	0
Asian	0	1	0	0
Native Hawaiian or Other Pacific Islander	0	0	0	0
Black or African American	0	0	0	0
White	3	6	0	0
More Than One Race	0	0	0	0
Total	3	7	0	0
				10

#### 7.0 RECORDS AND REPORTING

See the Case Report Forms posted on the COG web site with each protocol under “*Data Collection*”. A submission schedule is included.

##### 7.1 CDUS

This study will be monitored by the Clinical Data Update System (CDUS) Version 3.0. Cumulative protocol- and patient-specific CDUS data will be submitted quarterly to CTEP by electronic means. Reports are due January 31, April 30, July 31 and October 31. CDUS reporting is not a responsibility of institutions participating in this trial.

**APPENDIX I: CTEP AND CTSU REGISTRATION PROCEDURES****CTEP INVESTIGATOR REGISTRATION PROCEDURES**

Food and Drug Administration (FDA) regulations and National Cancer Institute (NCI) policy require all individuals contributing to NCI-sponsored trials to register and to renew their registration annually. To register, all individuals must obtain a Cancer Therapy Evaluation Program (CTEP) Identity and Access Management (IAM) account (<https://ctepcore.nci.nih.gov/iam>). In addition, persons with a registration type of Investigator (IVR), Non-Physician Investigator (NPIVR), or Associate Plus (AP) (i.e., clinical site staff requiring write access to OPEN, RAVE, or TRIAD or acting as a primary site contact) must complete their annual registration using CTEP's web-based Registration and Credential Repository (RCR) (<https://ctepcore.nci.nih.gov/rrc>). Documentation requirements per registration type are outlined in the table below.

Documentation Required	IVR	NPIVR	AP	A
FDA Form 1572	✓	✓		
Financial Disclosure Form	✓	✓	✓	
NCI Biosketch (education, training, employment, license, and certification)	✓	✓	✓	
HSP/GCP training	✓	✓	✓	
Agent Shipment Form (if applicable)	✓			
CV (optional)	✓	✓	✓	

An active CTEP-IAM user account and appropriate RCR registration is required to access all CTEP and CTSU (Cancer Trials Support Unit) websites and applications. In addition, IVRs and NPIVRs must list all clinical practice sites and IRBs covering their practice sites on the FDA Form 1572 in RCR to allow the following:

- Added to a site roster
- Assigned the treating, credit, consenting, or drug shipment (IVR only) tasks in OPEN
- Act as the site-protocol PI on the IRB approval
- Assigned the Clinical Investigator (CI) role on the Delegation of Tasks Log (DTL).

Additional information can be found on the CTEP website at:

<https://ctep.cancer.gov/investigatorResources/default.htm>. For questions, please contact the RCR **Help Desk** by email at [[contact]](mailto:[contact]).

## **CTSU REGISTRATION PROCEDURES**

This study is supported by the NCI Cancer Trials Support Unit (CTSU).

### **Requirements for ACCL10P1 Site Registration:**

- IRB approval (For sites not participating via the NCI CIRB; local IRB documentation, an IRB-signed CTSU IRB Certification Form, Protocol of Human Subjects Assurance Identification/IRB Certification/Declaration of Exemption Form, or combination is accepted )
- IROC Credentialing Status Inquiry (CSI) Form

NOTE: For studies with a radiation and/or imaging (RTI) component, the enrolling site must be aligned to a RTI provider. To manage provider associations access the Provider Association tab on the CTSU website at <https://www.ctsu.org/RSS/RTFProviderAssociation>, to add or remove associated providers. Sites must be linked to at least one IROC credentialed provider to participate on trials with an RT component.

### **Checking Your Site's Registration Status:**

You can verify your site registration status on the members' section of the CTSU website. (Note: Sites will not receive formal notification of regulatory approval from the CTSU Regulatory Office.)

- Go to <https://www.ctsu.org> and log in to the members' area using your CTEP-IAM username and password
- Click on the Regulatory tab at the top of your screen
- Click on the Site Registration tab
- Enter your 5-character CTEP Institution Code and click on Go

Note: The status given only reflects compliance with IRB documentation and institutional compliance with protocol-specific requirements as outlined by the Lead Network. It does not reflect compliance with protocol requirements for individuals participating on the protocol or the enrolling investigator's status with the NCI or their affiliated networks.

## APPENDIX II: COGMED RM AND COGMED JM

**Cogmed RM** and **Cogmed JM** are computer programs installable from a CD-ROM and compatible with any Windows-based computer or tablet device. They are commercially available to qualified practitioners through *Cogmed*; [name] has already received training and certification as a practitioner and has experience treating children on the NCI R03-CA132570 study. The program consists of twelve visually engaging and interesting exercises that target skills involving visuo-spatial and verbal WM. Difficulty of the tasks is automatically adjusted on a trial-by-trial basis throughout each training session to match a child's current memory span, such that as the child becomes more proficient, the exercises become more difficult. *Cogmed RM* is designed for children aged 8 to 16. Exercises have space and robot themes with names such as "Decoder," "Space Whack," and "Visual Data Link." For example, "Asteroids," a visuo-spatial WM exercise, consists of a number of asteroids floating through space. The asteroids light up in a random order, after which the child is asked to click on the asteroids in the order in which they just were highlighted. When done correctly, the highlighted asteroids explode. In "Stabilizer," a verbal memory exercise, children hear a series of letters while lights illuminate with each letter. Then, when the letter appears on the screen, the child must select the correct light that was originally paired with that letter. *Cogmed RM* also contains a game, "Robo Racing," that children can play at the end of each session as a reward for completing their session. Children are encouraged to perform well during their training session to earn more "energy" that can later be used during the reward game. *Cogmed JM* is the preschool version of the computer program, designed for children aged 4 to 7 years (see Figure 1 for an example exercise).

Figure 1 Cogmed JM activity – "Ferris Wheel"  
Adapted from [www.cogmed.com](http://www.cogmed.com)

In each version of the intervention, children complete 25 training sessions. Children are asked to complete between 3 and 5 sessions per week, so the total treatment time to complete 25 sessions may range from 5 to 9 weeks. For children completing *Cogmed RM*, sessions typically last between 25 and 45 minutes, depending on the child's working memory span. For younger children completing *Cogmed JM*, sessions are designed to be shorter in accordance with young children's cognitive stamina; thus, younger children's training sessions typically last about 15 minutes.

Throughout training, the child's intervention coach has online access to detailed information about his or her training sessions. Specifically, coaches can see when and how long children trained, and the outcome (pass or fail) of each of the trials children complete during a single training session. Using this information, coaches can modify the training sequence or make suggestions to the child and/or parent about how progress can be maximized (e.g., by taking a short break after three failed trials to prevent frustration). Families will have phone meetings at least once per week with an intervention coach to ensure compliance, track progress, provide feedback and answer any questions that may have arisen during treatment. Coaches will also have an assessment script for these calls, for re-evaluating medical, psychological, and environmental factors that may potentially be related to feasibility and efficacy of the intervention.

**Treatment compliance:** The *Cogmed* programs automatically track the number and length of children's sessions, along with their progress through program levels. This is accomplished through the Internet, every time the child logs into the program. For those families without home-internet access, they will be asked to connect the program after every 3rd session from a library or commercial establishment with free wireless internet access. To date, participants on our survivor trial (R03-CA132570) have had no difficulty uploading data over the course of the intervention, and thus we anticipate no difficulty in the proposed project. To promote compliance and maintain children's interest in the program, participants will earn a \$15 gift card (or comparably valued prize/compensation) for participating in the baseline testing. In addition, participants will earn \$10 gift cards (or comparably valued prizes/compensation) after session numbers 9, 18, and 25. The participant and their parent will each receive \$15 (gift cards/prizes) for completing the post-intervention and follow-up testing.

